16.6.4 Preparation and Administration

Refer to the pharmacy manual for product preparation instructions.

Pembrolizumab will be administered as a 30-minute IV infusion using an infusion pump (treatment cycles may be delayed for 3 weeks due to toxicity as described in Section 11). Sites should make every effort to target infusion timing to be as close to 30 minutes as possible. However, given the variability of infusion pumps from site to site, a window of -5 minutes and +10 minutes is permitted (i.e., infusion time is 30 minutes: -5 min/+10 min). Attach the infusion line to the pump and prime the line, either with normal saline (at least 25 mL) or with infusion solution as per local SOP, before

starting the infusion. Maximum infusion rate should not exceed 6.7 ml/min through a peripheral or indwelling catheter. Use 30 mL normal saline to flush the infusion line at the end of the infusion if institutional guidelines allow.

Unused infusion solution should not be used for another infusion of the same participant or a different participant.

DO NOT administer the product as an intravenous push or bolus.

DO NOT combine, dilute or administer it as an infusion with other medicinal products.

A central line is not required for Pembrolizumab administration, but may be used if available.

The following infusion set materials are compatible with Pembrolizumab

- PVC infusion set that is plasticized using Di-2-ethylhexyl Terephthalate DEHP
- PVC and tri-(2-ethylhexyl) trimellitate (TOTM) infusion set
- Polyethylene lined PVC infusion set
- Polyurethane
- Polybutadiene

A sterile, non-pyrogenic, low-protein binding 0.2 to 5 µm in-line filter made of polyethersulfone (PES) or polysulfone must be used during administration to remove any adventitious particles. If the infusion set does not contain a 0.2 to 5 µm in-line filter, it is recommended to use a 0.2 to 5µm add-on filter which may contain an extension line (the materials of the extension line and filter should be as mentioned above).

17.0 OUTCOME MEASUREMENTS

17.1 Criteria for Response, Progression, and Relapse (Solid Tumors)

Patients should be reevaluated by Response Evaluation Criteria in Solid Tumors (RECIST 1.1) after completion of neoadjuvant pembrolizumab. Unidimensional measurements in the largest diameter will be used.

17.1.1 Measurable Disease

Measurable lesions are defined as those that can be accurately measured (select largest, most reproducible lesions) in at least one dimension (largest diameter in the plane of measurement is to be recorded) as ≥ 20 mm with x-ray or ≥ 10 mm with CT scan (CT scan slice thickness ≤ 5 mm) or MRI. If scan has slice thickness > 5 mm, the minimum size for a measurable lesion should be twice the slice thickness. Measurable lesions will also include those that can be directly measured on physical exam with calipers and are at least 10 mm. Lesions which cannot be accurately measured

with calipers should be recorded as non-measurable. All tumor measurements must be recorded in millimeters (or decimal fractions of centimeters).

17.1.2 Non-Measurable Disease

All other lesions (or sites of disease), including small lesions (longest diameter <20 mm with x-ray or <10 mm using CT or MRI scan), are considered non-measurable disease. Lesions considered non-measurable include: bone lesions, leptomeningeal disease, ascites, pleural/pericardial effusions, lymphangitic involvement of skin or lungs, inflammatory breast disease, abdominal masses/abdominal organomegaly identified by physical exam that is not measurable by reproducible imaging techniques.

17.1.3 Target Lesions

All measurable lesions up to a maximum of two lesions per organ (total 5 maximum target lesions) are considered target lesions. Target lesions should be selected on the basis of their size (lesions with the longest diameter) and their suitability for accurate repeated measurements (either by imaging techniques or clinically). A sum of the longest diameter (LD) for all target lesions will be calculated and reported as the baseline sum LD.

The baseline sum LD will be used as reference by which to characterize the objective tumor response.

17.1.4 Non-Target Lesions

All other lesions (or sites of disease) should be identified as non-target lesions and should also be recorded at baseline. Non-target lesions include measurable lesions that exceed the maximum numbers per organ or total of all involved organs as well as non-measurable lesions. Measurements of these lesions are not required but the presence or absence of each should be noted throughout follow-up.

17.2 Guidelines for Evaluation of Measurable/Evaluable Disease

If subject has measurable disease, all measurements should be taken and recorded in metric notation. For subjects with evaluable disease only, the sites of disease will be noted at baseline and followed for increase or decrease in size and/or new disease. All baseline evaluations should be performed as closely as possible to the beginning of treatment and never more than 30 days before the beginning of the treatment, unless otherwise specified. The same method of assessment and the same technique should be used to characterize each identified and reported lesion at baseline and during follow-up. Imaging-based evaluation is preferred to evaluation by clinical examination when both methods have been used to assess the antitumor effect of a treatment.

Clinical lesions: Clinical lesions will only be considered measurable when they are superficial and ≥ 10 mm diameter as assessed using calipers (e.g., skin nodules). In the case of skin lesions, documentation by color photography, including a ruler to estimate the size of the lesion, is recommended.

CT and MRI: These techniques should be performed with cuts of 5 mm or less in slice thickness contiguously. If scan has slice thickness > 5 mm, the minimum size for a measurable lesion should be twice the slice thickness. CT is currently the best available and reproducible method to measure lesions for response assessment.

Cytology, Histology: These techniques can be used to differentiate between partial responses (PR) and complete responses (CR) in rare cases (e.g., residual lesions in tumor types, such as germ cell tumors, where known residual benign tumors can remain).

17.3 Response Criteria

Evaluation of Target Lesions

Complete Response (CR): Disappearance of all target lesions

Partial Response (PR): At least a 30% decrease in the sum of the largest diameter (LD) of target lesions, taking as reference the baseline sum LD

Progressive Disease (PD): At least a 20% increase and a 5 mm absolute increase in the sum of the LD of target lesions, taking as reference the smallest sum LD recorded since the treatment started or the appearance of one or more new lesions. If scan showing new lesion is of anatomical region which was not included in baseline scans, it is PD.

Stable Disease (SD): Neither sufficient shrinkage to qualify for PR nor sufficient increase to qualify for PD, taking as reference the smallest sum LD since the treatment started

Evaluation of Non-Target Lesions

Complete Response (CR): Disappearance of all non-target lesions and normalization of tumor marker level

Incomplete Response/Stable Disease (SD): Persistence of one or more non-target lesion(s) and/or maintenance of tumor marker level above the normal limits

Progressive Disease (PD): Appearance of one or more new lesions and/or unequivocal progression (not attributable to different scanning technique or non-tumor) of existing non-target lesions. ('Unequivocal progression' must be an overall level of substantial worsening in non-target disease that is of a magnitude that, even in the presence of SD or PR in target disease, the overall tumor

burden has increased sufficiently to merit discontinuation of therapy.) If scan showing new lesion is of anatomical region which was not included in baseline scans, it is PD.

Table 4: Evaluation of Best Overall Response

Target Lesions	Non-Target Lesions	New Lesions	Overall Response
CR	CR	No	CR
CR	Non-CR/non-PD	No	PR
CR	Not evaluated	No	PR
PR	Non-PD	No	PR
SD	Non-PD	No	SD
PD	Any	Yes or No	PD
Any	PD	Yes or No	PD
Any	Any	Yes	PD

17.3.1 Immune-Related Tumor Assessment

Pembrolizumab is an immuno-stimulating antibody with evidence of anti-cancer activity (durable objective response and stable disease) in subjects with advanced melanoma, including subjects with established brain disease. Observations of clinical activity defined by tumor response endpoints defined by conventional criteria (e.g., mWHO) may be inadequate to realize the kinetics and magnitude of clinical benefit achieved with pembrolizumab.

Histopathologic evidence has demonstrated pembrolizumab can produce an influx or expansion of tumor infiltrating lymphocytes. Therefore, early increases in lesion size detected radiologically or upon gross examination could be misinterpreted as progressive tumor growth and precede objective tumor shrinkage. In addition, the appearance of new lesions may have categorized a subject to have progressive disease using conventional tumor assessment criteria despite the concurrent observation of objective tumor responses in pre-existing lesions and a net reduction in global tumor burden that includes the new lesions.

Therefore, patients with evidence of possible target lesion growth or new lesion appearance will not be presumed to have progressed and will proceed to surgery as long as all possible site of disease are deemed resectable by the surgeon.

17.4 Cytology and Histology

If the measurable disease is restricted to a solitary lesion, its neoplastic nature should be confirmed by cytology/histology. These techniques can be used to differentiate between PR and CR in rare cases (for example, residual lesions in tumor types such as germ cell tumors, where known residual benign tumors can remain). The cytological confirmation of the neoplastic origin of any effusion that appears or worsens during treatment when the measurable tumor has met criteria for response or stable disease is mandatory to differentiate between response or stable disease (an effusion may be a side effect of the treatment) and progressive disease.

17.5 Pathologic Response Criteria

After receiving preoperative pembrolizumab, criteria for examining resected tumor will be as follows:

- No Response: no evidence of cell death or tumor necrosis.
- Partial Response: $\geq 30\%$ tumor necrosis or cell death.
- Complete Response: no evidence of viable tumor in surgical specimen (includes lung tissue and dissected lymph nodes)

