6.2 Inclusion Criteria

Patients are eligible to be included in the study only if they meet **all** of the following criteria. For time limits on imaging and blood tests see study calendar:

1. Histologically cytologically confirmed NSCLC.
2. Clinical stage IB (≥ 3 cm per CT), Stage IIA/IIB, or Stage IIIA (N0-2) amenable to surgical resection.
3. Primary tumor ≥ 3 cm (for all stages entered) to increase the likelihood that excess tumor will be available after resection.
4. Patient must be deemed a surgical candidate as documented by surgeon within their respective institutional standards.
5. ECOG performance status of 0 or 1 (Appendix C).
6. NO prior chemotherapy, radiation therapy or biologic/targeted therapy for current diagnosis of lung cancer.
7. Age ≥ 18 years.
8. No active invasive malignancy in the past 2 years other than non-melanoma skin cancer. Cancers that are in-situ are not considered invasive.
9. Signed written informed consent including HIPAA according to institutional guidelines.
10. Adequate Organ Function:

System	Laboratory Value
Hematological	
Absolute neutrophil count (ANC) or AGC	≥ 1500 per uL
Platelets	$\geq 100,000$ per uL
Hemoglobin	≥ 9 g/dL or ≥ 5.6 mmol/L without transfusion or EPO dependency (within 7 days of assessment)
Renal	

Serum creatinine OR Measured or calculated creatinine clearance (GFR can also be used in place of creatinine or CrCl)	≤ 1.5 X upper limit of normal (ULN) OR ≥ 60 mL/min for subject with creatinine levels > 1.5 X institutional ULN
Hepatic	
Serum total bilirubin	≤ 1.5 X ULN OR
	Direct bilirubin \leq ULN for subjects with total bilirubin levels > 1.5 ULN
AST (SGOT) and ALT (SGPT)	≤ 2.5 X ULN
Albumin	≥ 2.5 mg/dL
Coagulation	
International Normalized Ratio (INR) or Prothrombin Time (PT)	≤ 1.5 X ULN unless subject is receiving anticoagulant therapy as long as PT or PTT is within therapeutic range of intended use of anticoagulants
Activated Partial Thromboplastin Time (aPTT)	≤ 1.5 X ULN unless subject is receiving anticoagulant therapy as long as PT or PTT is within therapeutic range of intended use of anticoagulants
^a Creatinine clearance should be calculated per institutional standard. (Appendix D)	

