- 1) We will estimate the rate of objective response rate for the protocol treatment. The definition of objective response will be measured by RECIST 1.1. The objective response rate (ORR=CR+PR) along with its 95% exact confidence interval will be estimated.

- 2) We will evaluate disease-free survival and patterns of metastases after protocol treatment. Disease-free survival (DFS) is defined as the time from surgical resection to disease recurrence (first disease recurrence or death, whichever comes first) after surgery. The Kaplan-Meier estimator will be used to estimate median DFS and its confidence interval. The frequencies of metastases by site will be tabulated.
- 3) Blood based biomarkers will be evaluated for the changes before and after the protocol treatment. The association of the baseline value and the changes of these biomarkers with clinical outcomes, such as objective response, overall survival and disease free survival, will be evaluated using logistics regression and Cox models.
- 4) We will determine the percentage of patients with “detectable” (percentage of $\geq 0.05\%$ with each value also being at least twice that of the background unstimulated control value) tumor infiltrating lymphocytes (TILs) after protocol treatment. The percentage of patients with TILs for patients who have surgical resection and its exact confidence interval will also be estimated.
- 5) We will evaluate whether presence, quantity or quality of detectable TILs is associated with pathologic response to neoadjuvant therapy. A Fisher exact test will be used to evaluate the association of both the presence and the quality of TILs with pathologic tumor response to neoadjuvant therapy. A Wilcoxon rank sum test will be used to test the association of the quantity of TILs and pathologic response to neoadjuvant therapy.
- 6) Treatment-related adverse events will be summarized by type and grade.
- 7) The proportion of patients with detectable circulating T cells specific against TAA after the protocol treatment will be estimated and its confidence interval will be provided. An exact binominal test will be used to test the increase in the proportion of patients with detectable circulating T cells specific against TAA after the protocol treatment relative to baseline.
- 8) Estimate the rate of pathologic response for neoadjuvant pembrolizumab in early stage NSCLC. The pathologic response rate along with its 95% exact confidence interval will be estimated.

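### Partial pathologic response is scored on necrosis but complete response on viable tumour, with no baseline or control: necrosis of 30% or more present before dose 1 is credited to pembrolizumab, and tumours above 0% but under 30% fit no category

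*Combined protocol and SAP*

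**What the plan says.** Section 17.5 opens with "After receiving preoperative pembrolizumab, criteria for examining resected tumor will be as follows" and gives three categories:

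- "No Response: no evidence of cell death or tumor necrosis".
- Partial Response: at least 30% "tumor necrosis or cell death".
- "Complete Response: no evidence of viable tumor in surgical specimen (includes lung tissue and dissected lymph nodes").

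Before treatment, Section 6.2 asks for histologic or cytologic confirmation of NSCLC and "Primary tumor ≥ 3 cm (for all stages entered"). Section 9.1 lists tumour histology at screening. Neither asks for a reading of necrosis or viability. In the Appendix A schedule, the row for tumour biopsy slides is marked only at surgery. Section 3.1 states that there is no treatment control.

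Section 27.1, item 8, sets out to "Estimate the rate of pathologic response for neoadjuvant pembrolizumab in early stage NSCLC", with a 95% exact confidence interval; Section 4.2 has the same objective. Item 5 tests TIL presence, quality and quantity against pathologic response, and item 9 does so for T-cell reactivity. Appendix B summarises changes by response status as yes or no and does not say where the three categories are split.

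**The concern.** Item 8 attributes the rate to neoadjuvant pembrolizumab, but the Partial Response criterion has no baseline term and the trial has no comparator. Nothing in the plan can show that 30% necrosis seen at resection was absent before dose 1.

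The opposite error is also possible. Section 17.3.1 says "pembrolizumab can produce an influx or expansion of tumor infiltrating lymphocytes". If part of a tumour is replaced by infiltrate or scar while some viable tumour remains, the lost tumour is credited only so far as it shows as necrosis or cell death.

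Both errors, and the unclassified band, carry into items 5, 8 and 9 and the Appendix B summaries, because all of them rest on this one definition.

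**Working it through.** The documents state no expected rate, power or sample size for pathologic response, so there is no planned figure to reproduce. The check is a reading of the criteria, followed by a sensitivity calculation.

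**The categories side by side**

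| Specimen | Category under 17.5 |
|---|---|
| 0% necrosis or cell death, viable tumour present | No Response |
| Above 0%, under 30%, viable tumour present | none |
| 30% or more, viable tumour present | Partial Response |
| No viable tumour, any amount of necrosis | Complete Response |

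Two scales are mixed. A tumour with 30% necrosis and 100 − 30 = 70% viable is a partial responder. A tumour with 29% necrosis, whose remaining 100 − 29 = 71% is nearly all scar, is not, although far less viable tumour is left. That second result holds unless cell death is read to include cells already cleared; 17.5 does not define the term.

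**Necrosis that predates treatment**

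Let r be the true drug response rate and q the share of the other tumours that already had at least 30% necrosis. Both are assumptions. The reported rate is r + (1 − r)q.

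| r | q = 5% | q = 10% | q = 20% | q = 30% |
|---|---|---|---|---|
| 0% | 5% | 10% | 20% | 30% |
| 10% | 14.5% | 19% | 28% | 37% |
| 20% | 24% | 28% | 36% | 44% |

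For example, 0.20 + 0.80 × 0.05 = 0.24 and 0.20 + 0.80 × 0.30 = 0.44. With no drug effect and q = 20%, the expected count in the 30 evaluable patients is 6, and 6/30 has an exact 95% interval of 7.7% to 38.6%.

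For counts, assume 24 resected patients (30 evaluable × the 0.80 historical rate in Section 27.1) and no drug effect. The chance of 3 or more apparent responders is 12%, 44% and 89% at q = 5%, 10% and 20%.

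**Partial regression without enough necrosis**

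If a share m of true responders is missed, the reported rate is r(1 − m) + [1 − r(1 − m)]q. For r = 20%:

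- q = 0: m = 25% gives 15%, and m = 50% gives 10%.
- q = 5%: m = 25% gives 0.15 + 0.85 × 0.05 = 19.3%, and m = 50% gives 0.10 + 0.90 × 0.05 = 14.5%.
- q = 30%: m = 25% gives 40.5%, and m = 50% gives 37%.

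The net error can therefore go either way.

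**The TIL comparison**

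Assume r = 20%, TILs detected in 70% of true responders and 20% of the rest, and earlier necrosis unrelated to TILs. The true difference is 50 points. At q = 10% the labelled responders are 0.20 true and 0.80 × 0.10 = 0.08 false. Detection among them is (0.20 × 0.70 + 0.08 × 0.20)/0.28 = 56%, and the difference falls to 36 points. At q = 20% it is (0.14 + 0.16 × 0.20)/0.36 = 48%, a difference of 28 points.

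**The case against.** The strongest reply is that this is a small matter. Section 27.1 calls all secondary objectives exploratory. The rate is only estimated, with no hypothesis or decision attached, and the surgery feasibility endpoint does not use it. All of that stands, and it limits the weight of the point.

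Four stronger readings are tempting, and the documents do not support them:

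- A reader might infer that response is scored on necrosis alone, so that clearance without necrosis never counts. Complete Response is defined by viability and needs no necrosis, so complete clearance counts.
- A reader might infer that any spontaneous necrosis inflates the rate. Only 30% or more does.
- A reader might infer that the size rule selects necrotic tumours. Section 6.2 gives tissue supply as its reason, "for all stages entered) to increase the likelihood that excess tumor will be available after resection", and no section links size to necrosis.
- A reader might take Section 17.3.1 to say that response occurs without cell death. It mentions lymphocyte influx to explain apparent growth, and says nothing about how tumour cells are lost.

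It can also be objected that residual viable tumour has the same weakness: if the components sum to 100%, earlier necrosis lowers the viable share as well. That is correct, and the fix must say so. Finally, the plan does not describe how the tumour bed is sampled or who reads it at each institution, and Appendices H and I take at least 1 gm of tumour fresh for TILs. Any percentage therefore describes only the tissue sampled.

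**Conclusion.** The point holds as a defect of definition in an exploratory endpoint and is worth correcting. Three things follow from the text alone: the mixed scales, the missing category between 0% and 30%, and the unstated yes/no cut. That pre-treatment necrosis of 30% or more would be scored as a partial response follows from the absence of a baseline reading and a control.

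The size of the bias is not known. The 24% to 44% for a true 20% rests on an assumed background share of 5% to 30%, applied equally to tumours that did not respond, with no true responders missed. The 12%, 44% and 89% also rest on the assumed 24 resections. The weakening of the TIL comparison illustrates the mechanism under stated detection rates and is not an estimate for this trial. If earlier necrosis is itself related to TILs, the distortion could differ in direction.

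**What to change.** Amend Section 17.5 and items 5, 8 and 9 of Sections 4.2 and 27.1:

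1. On the resection slides, record percent viable tumour, percent necrosis and percent stroma/inflammation, summing to 100%. State how the tumour bed was sampled.
2. Define response categories on percent residual viable tumour that cover every value from 0% to 100% without overlap. Fix the yes/no cut before any slide is read, and use the same cut in Appendix B.
3. Use the categories for the rate in item 8. Use percent residual viable tumour as a continuous measure for the associations in items 5 and 9, which also avoids dichotomising in a small sample.
4. Report the rate at the 30% necrosis cut as a secondary description.
5. State that neither measure can fully separate pre-treatment necrosis from drug effect without a baseline or control. Use the recorded necrosis component in a sensitivity analysis, for example by repeating item 8 with responders who qualify mainly through necrosis counted as non-responders.

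The cost is a longer reading form and some loss of comparability with a necrosis-based rate, which is why that rate is kept. No extra biopsy is needed and patient care does not change.

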17.6 Disease-Free Survival

Disease-free survival (DFS) is defined as the time from surgical resection to disease recurrence (first disease recurrence or death, whichever comes first) after surgery.

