17.7 Survival

Survival will be measured from the date of enrollment.

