27.0 STATISTICAL METHODS AND ANALYTICAL PLANS

27.1 Statistical Considerations

Sample size justification

Futility Analysis

Futility analysis is often used for assessing clinical efficacy before the trial reaches target accrual and stops the trial early if the therapy clearly performs worse than control. The primary objective of this one-arm phase II trial is not to evaluate the efficacy of pembrolizumab in this population. Since it is unlikely that the therapy will harm the patients, a futility analysis on the percentage of patients with adequate TIL collection is unnecessary.

Evaluation of Investigational Therapy Safety and Feasibility

Analytic methods

Overview

The primary objective of the single arm phase II trial is to determine whether the surgery feasibility rate of neoadjuvant pembrolizumab is not significantly worse than the historical surgical feasibility rate of neoadjuvant chemotherapy. Surgery feasibility rate of a neoadjuvant therapy is the percent of patients who are able to undertake surgery after the neoadjuvant therapy. A total of 30 evaluable patients will be entered to the single arm trial. Taking 15% rate of cancellation and ineligibility into account, the trial will enroll a total of 35 patients and eligible subjects (not screen failures) will be followed for 2 years for both disease recurrence and death. Following that, patients will be followed every 6 months for up to five years.

Primary Objective Sample Size Justification

According to Pisters et al (JCO 2010), approximately 80% of subjects undergo surgical exploration within 42 days of day 1 of the last cycle of standard neoadjuvant chemotherapy. We would like to test the following hypotheses:

$$H_0: p \geq 0.80 \text{ vs. } H_a: p \leq 0.65$$

where p is the true surgery feasibility rates after combined neoadjuvant chemotherapy and pembrolizumab. With 30 evaluable patients receiving protocol treatment, the study has approximately 84.6% power rejecting $H_0: p \geq 0.80$ when $p = 0.65$ at one-sided significance level of 15%.

Adverse event monitoring: In this trial design it is difficult to accurately attribute adverse events to pembrolizumab, surgery, or other causes. Further, the analysis of treatment toxicities as isolated events will not best represent whether or not the combination of pembrolizumab followed by surgery is safe and feasible. Therefore, this safety and feasibility trial will be evaluated by the following criteria:

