- 1) Whether the cumulative percentage of deaths among all treated patients related to any of the study treatments from the first pembrolizumab treatment until 30 days after surgery exceeds 17%.
- 2) If the cumulative percentage of all treated patients deemed unable to go to surgery due to adverse events attributed to neoadjuvant therapy exceeds 20%. The percentage of patients unable to go to surgery after pembrolizumab is a conservative estimate based on data reported for a SWOG trial that studied neoadjuvant chemotherapy in early stage lung cancer (22).

The first 10 treated patients will be evaluated for safety and feasibility. If in the first ten patients the criteria for overall therapy being not safe or feasible is met, accrual to the study will be suspended to allow for investigation. After consideration by the study team and the IRB, a decision will be made as to whether accrual can be resumed, potentially with modifications to entry criteria and/or study conduct. In addition, all toxicity patterns will be monitored by the DCI Safety Oversight Committee.

The trial will be stopped for accrual whenever a total of 35 patients are registered or at least one of the thresholds of the safety and feasibility criteria is exceeded. In the event either of these two thresholds is exceeded, the investigational therapy will be considered “infeasible” in this setting.

Accrual and follow-up

With an expected rate of 2 patients being enrolled each month, the trial will take about 16 months to reach the target accrual. All registered patients will be followed for tumor response, disease free survival and overall survival.

Statistical Analysis Plan

Surgery feasibility rate, the primary endpoint of the trial, will be analyzed using the data from all evaluable patients, who are defined as the patients who meet eligibility criteria and has received at least 1 dose of pembrolizumab. The surgery feasibility rate of neoadjuvant pembrolizumab as well as its confidence interval will be estimated.

Secondary Objectives

All secondary objectives are considered exploratory in nature, and type I error will not be controlled for multiplicity. P-values for these statistical tests will be provided for descriptive purposes. However, if a statistical test on a secondary outcome is significant at the 2-sided significance level of 0.01, the finding will be considered worthy of future investigation.

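### DFS starts at resection, so death or progression before surgery never counts in the only defined time-to-recurrence endpoint, although the plan promises DFS follow-up for every registered patient

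*Combined protocol and SAP*

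**What the plan says.** The definition is the same in Section 4.2 (item 2), Section 17.6 and Section 27.1 (Secondary Objectives, item 2): "Disease-free survival (DFS) is defined as the time from surgical resection to disease recurrence", where the event is the earlier of recurrence and death following the operation. Item 2 introduces the analysis with "We will evaluate disease-free survival and patterns of metastases after protocol treatment" and continues: "The Kaplan-Meier estimator will be used to estimate median DFS and its confidence interval". No section gives a start date, event, censoring rule or analysis set for a patient without a resection.

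Three other statements bear on this:

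- Section 27.1, Accrual and follow-up: "All registered patients will be followed for tumor response, disease free survival and overall survival".
- Section 17.7: "Survival will be measured from the date of enrollment".
- Section 27.1, Secondary Objectives, item 3: baseline values and changes in blood biomarkers are related to objective response, overall survival and DFS by logistic and Cox models. Section 10.1 places the baseline sample before treatment starts.

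The primary endpoint counts who reaches surgery: "Surgery feasibility rate of a neoadjuvant therapy is the percent of patients who are able to undertake surgery after the neoadjuvant therapy". Section 27.1 analyses it in all evaluable patients, meaning eligible patients with at least one dose. PFS is named as a biomarker outcome in Sections 1.5 and 5.1.3, but neither Section 17 nor Section 27.1 defines it.

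**The concern.** Protocol treatment begins with neoadjuvant pembrolizumab, but the DFS clock begins only at resection. A patient who dies, progresses beyond resectability or becomes unfit in between has neither time at risk nor an event. The Kaplan-Meier curve then describes only patients who got through the neoadjuvant phase, and the less feasible the regimen proves, the more selected that group becomes.

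This contradicts the sentence promising DFS follow-up for all registered patients. It also affects the biomarker models. A marker measured before the first dose would be related to DFS only in patients who later reached surgery, which conditions on a post-baseline event that the marker may itself predict. The same marker would be related to overall survival in everyone, from a different time zero.

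**Working it through.** **1. Does any section supply DFS for an unresected patient?** No.

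- Section 9.6 takes patients whose resection was not attempted off protocol therapy and says nothing about DFS.
- Section 9.5 removes patients not operated on in days 29-56 unless the PI approves, again without a DFS rule.
- The TIL percentage (item 4) is explicitly restricted to patients who have a resection. DFS carries no such label.

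**2. Does the plan foresee patients not reaching surgery?** Yes. That share is the complement of the primary endpoint. The feasibility rule in Section 27.1 is met only when more than 20% of treated patients cannot have surgery because of adverse events attributed to neoadjuvant therapy, so the trial can run on with some loss.

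**3. How many would lack DFS at the design values?** Inputs from Section 27.1: N = 30 evaluable; p = 0.80 (boundary of the null) and p = 0.65 (alternative). The plan states no figure for this share. Number without DFS = N × (1 − p):

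- p = 0.80: 30 × 0.20 = 6, leaving 24.
- p = 0.65: 30 × 0.35 = 10.5, leaving 19.5.

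The chance that all 30 are operated on is p^30: 0.80^30 = 0.0012, and 0.65^30 = 0.000002. At either value, some missing DFS is almost certain.

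(The stated power of 84.6% uses the same inputs but plays no part here. It does not reproduce at N = 30: an exact binomial test rejecting at 21 or fewer has power 77.5% at attained alpha 0.129. That is a separate matter.)

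**4. How far could DFS and an all-patient result differ?** Let S be the proportion of resected patients event-free at 2 years. The documents give no value, so S = 50% to 80% is assumed. If no unoperated patient stays event-free, the all-patient proportion is p × S, and the gap is S × (1 − p).

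| Assumed S | p × S at p = 0.80 | gap (points) | p × S at p = 0.65 | gap (points) |
|---|---|---|---|---|
| 50% | 40% | 10 | 32.5% | 17.5 |
| 60% | 48% | 12 | 39% | 21 |
| 70% | 56% | 14 | 45.5% | 24.5 |
| 80% | 64% | 16 | 52% | 28 |

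The p × S columns are floors: any unoperated patient who stays event-free raises the all-patient figure and narrows the gap. Moving time zero back to enrolment does not lower the floor, because 2 years from enrolment falls earlier than 2 years from surgery for resected patients.

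**5. Are the data for an all-patient endpoint secured?** Not fully.

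- Section 9.8.6 schedules outcome collection relative to surgery.
- Section 15.1 ends disease-status follow-up at the start of non-study cancer treatment for patients who discontinue without progression.
- Section 19.3.3 moves patients to survival follow-up once new therapy begins.

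An unoperated patient given other therapy may therefore have no recorded progression date.

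**The case against.** The strongest reply is that unoperated patients are not hidden. Failure to reach surgery is the primary endpoint, in all evaluable patients. Overall survival starts at enrolment. Objective response is assessed after neoadjuvant treatment (Section 17.1) and does not require surgery. Item 3 already relates biomarkers to both. DFS is a descriptive, exploratory estimate with no hypothesis or comparator, its definition says openly that it starts at resection, and a resected-only DFS is a coherent quantity. All of this stands. It limits the importance of the point and is why DFS from surgery should be kept. It does not reconcile the definition with the follow-up sentence, nor supply a time-to-recurrence result for the whole regimen.

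Three stronger readings are tempting, and the documents do not support them:

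- *That the plan expects 20% to 35% never to be operated on.* The null is p of at least 0.80, so it allows fewer; 0.65 is the value at which power is calculated. The 80% is a historical rate of exploration within 42 days, so some of the remainder may be operated on later, and the PI may approve surgery outside the window. Conversely, patients explored but not resected also lack DFS.
- *That everything the trial says about disease control rests on surgical successes.* This is true of DFS only.
- *That p × S estimates the all-patient result.* It is a floor under an assumed S. Section 9.6 sends patients whose resection was not attempted to standard oncology care, and some may stay event-free.

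**Conclusion.** The point holds in limited form. The DFS definition leaves out every patient without a resection, contradicts the statement that all registered patients are followed for DFS, and makes the baseline biomarker analysis of DFS conditional on reaching surgery. Because it omits death and progression before surgery, the result favours the regimen.

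At the design values, about 6 or 10 to 11 of 30 patients would be missing. Under the assumed 50% to 80% event-free at 2 years among resected patients, DFS would exceed an all-patient figure by at most 10 to 16 percentage points at p = 0.80 and 17.5 to 28 at p = 0.65. Those sizes rest on the design values, the assumed range and the extreme assumption that no unoperated patient stays event-free. The primary conclusion is unaffected. The change is still worth making, because no other defined endpoint fills the gap.

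**What to change.** 1. Label DFS from surgery as a resected-only summary in Sections 4.2, 17.6 and 27.1, and reword the follow-up sentence in Section 27.1 to match.
2. Add event-free survival from enrolment, the same time zero as overall survival, in all evaluable patients as Section 27.1 defines them, by Kaplan-Meier. Events: progression that precludes surgery; progression at any later time in a patient never resected; recurrence after resection; death from any cause. The third and fourth alone would miss later progression in patients not operated on because of toxicity or refusal. In line with Section 15.1, growth on CT alone before surgery is not an event.
3. State how patients who start non-study therapy without progression are handled, with a sensitivity analysis that counts this as an event.
4. Use event-free survival alongside overall survival in the Cox models for baseline biomarkers.

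Cost: SAP wording, one further Kaplan-Meier analysis, and a short protocol clarification that disease-status collection continues for unoperated patients, since Sections 9.8.6, 15.1 and 19.3.3 may otherwise end it or leave it unscheduled. No change to sample size or treatment is needed.
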